### 6.3.3 Additional Secondary Endpoint Analysis

#### 6.3.3.1 Number of Convulsive Seizure Free Days

Convulsive seizure free days will be taken from the parent/caregiver diary data.

A convulsive seizure free day will be defined as a day for which diary data are available and no convulsive seizures have been reported. The total number of convulsive seizure free days will be summed for the entire T+M period and similarly for the baseline period.

Seizure free days per 28 days at baseline = (number of seizure free days during baseline)\*28/(number of days during baseline with non-missing diary data)

Seizure free days per 28 days during T+M Period = (number of seizure free days during T+M Period)\*28/(number of days during T+M Period with non-missing diary data)

Statistical comparison of treatment groups and placebo on the number of seizure free days per 28 days during T + M using the baseline as covariate will be done with a similar approach as the primary analysis.

#### 6.3.3.2 Responder Analyses: Proportion with ≥25, or 75% Reduction from Baseline in Convulsive Seizure Frequency

A response curve will be generated for the mITT population. This graph will plot the % of subjects (y-axis) against percentage reduction in seizure frequency per 28 days in the T+M period (x-axis). The horizontal axis will be the % reduction, and the vertical axis will be the % of subjects achieving ≥ that % reduction. In the graph, subjects experiencing an increase or no decrease in seizure frequency (i.e., ≤0 % reduction) will be regarded as having a 0% reduction in seizure frequency. Hence the ordinate for the 0 time point may not necessarily be at 100%. For example, if 15% of subjects have no reduction in seizure frequency during T+M period compared to the baseline period, the graph will start on the y-axis at 85%. The graph will be generated for all subjects, by treatment group.

- The proportion achieving a ≥25% reduction from baseline in convulsive seizures will be analyzed for both treatment groups (ZX008 0.2 mg/kg/day and ZX008 0.8 mg/kg/day)

comparing independently with placebo, using the same method employed for the  $\geq 50\%$  reduction from baseline endpoint.

- The proportion achieving a  $\geq 75\%$  reduction from baseline in convulsive seizures will be analyzed for both treatment groups (ZX008 0.2 mg/kg/day and ZX008 0.8 mg/kg/day) comparing independently with placebo, using the same method employed for the  $\geq 50\%$  reduction from baseline endpoint.

A second response curve will be generated in which subjects who experience an increase in seizure frequency will be represented on the curve at horizontal axis at the position representing their increase in seizure frequency. Increases in seizure frequency will be represented to the left of the vertical axis on the figure.

### **6.3.3.3 Change from Baseline in Non-Convulsive Seizure Frequency**

Algorithms for calculating mean non-convulsive seizure frequency and percent change from baseline will follow the methods as described for the primary endpoint using a nonparametric ANCOVA to analyze the data, with ranks of the baseline non-CSFB as a covariate and ranks of non-CSFT+M as response,.

Change from baseline in non-convulsive seizures will be presented by seizure types (e.g., focal, generalized).

### **6.3.3.4 Change from Baseline in Convulsive + Non-Convulsive Seizure Frequency**

The change from baseline in convulsive + non-convulsive seizure frequency will be calculated as described for the primary endpoint, but considering both convulsive and non-convulsive seizures.

Algorithms for calculating mean convulsive and non-convulsive seizure frequency and percent change from baseline will follow the methods as described for the primary endpoint using a nonparametric ANCOVA to analyze the data, with ranks of the baseline convulsive + non-CSFB as a covariate and ranks of convulsive + non-CSFT+M as response,

### **6.3.3.5 Incidence of Rescue Medication Usage**

Use of rescue medication is recorded on the daily diary. In the event of prolonged seizures or status epilepticus, rescue medication is administered according to each subject's personalized regimen consisting of one or more medications. If the first rescue administration does not control the seizures, a second or even third round might be administered. They second and third round might use different medications or different doses than the first round of rescue meds.

Rescue medication will be summarized by treatment group and by active treatment vs. Placebo for the following:

- The number of days rescue medication was taken (normalized to 28 days) will be summarized separately for the Baseline and T+M periods by the mean (SD) as well as the median and range. Multiple medications taken on the same day will be counted once for that day. The ZX008 group will be compared to the placebo group using a rank ANCOVA analogous to that described in [Section 6.3.1.1](#). Specifically, the rank ANCOVA will use the ranks of rescue medication frequency during T+M as the response, and will incorporate treatment group as a factor and the ranks of rescue medication frequency during Baseline as a covariate.

- The number of medications used per episode will be summarized using similar descriptive statistics as above. Rescue medications related to an episode of SE are considered to be all rescue administered on the day of the SE (or seizure lasting >10 min). If more than one episode of SE or a seizure lasting >10 min occurred in a single day, the rescue medication for that episode is all rescue administered after the seizure until the start time of the next prolonged seizure.

#### **6.3.3.6 Incidence of Hospitalization to Treat Seizures**

Hospitalization data will be captured in the CRF and will be used to calculate incidence.

The number and percentage of subjects who utilized medical center care to treat a seizure will be presented by treatment group for the T+M period. Statistical comparisons of the differences between treatment and placebo groups will be based on Cochran-Mantel-Haenszel test stratified by age group.

#### **6.3.3.7 Incidence of Status Epilepticus**

The incidence of status epilepticus will be evaluated based on cases captured as such with treatment at hospitals or other treatment centers, those entered as adverse events (including SAEs) into the safety database, and also as convulsive seizures lasting longer than 10 min from the seizure diary. A single seizure meeting more than one of these criteria will be counted once. According to the ILAE, seizures of this duration are to be considered SE.

The number and percentage of subjects with status epilepticus recorded as an AE will be presented by treatment group for the baseline and the T+M period per 28 days. Statistical comparisons of the differences between treatment and placebo groups will be based on Fisher's exact test.

In addition, from the diary data, change from baseline in the number and percentage of convulsive seizures with duration >10 min for the baseline and T+M period will be reported. The number and percentage of subjects will be presented by treatment group for the baseline and the T+M period per 28 days. Statistical comparisons of the differences between treatment and placebo groups will be based on Fisher's exact test.

All seizures recorded in the AE database as status epilepticus should also be included in the seizure diary. An edit check will be performed to identify the overlap between seizures identified as AE of SE and seizures entered into the diary as seizures > 10 min. The "calculated" number and percentage of subjects experiencing SE will be presented by treatment group, defined as individuals who experience either an AE of SE, medical treatment for SE, or a seizure lasting longer than 10 min. Each subject will be represented once regardless of incidence. Statistical comparisons of the differences between treatment and placebo groups will be based on Fisher's exact test.

A second calculation will present the number of incidences of SE, according to the above definition, by treatment group normalized to per 28 days. In this analysis, a single subject may have more than one episode of SE, but an episode of SE recorded as both an AE and as a seizure longer than 10 min will be counted as a single episode. Statistical comparisons of the differences between treatment and placebo groups will be based on Fisher's exact test.

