## **6. STATISTICAL METHODOLOGY**

### **6.1 STATISTICAL AND ANALYTICAL ISSUES**

#### **6.1.1 Statistical Methods**

Tabulations for Study 1 will be produced for appropriate demographic, baseline, efficacy and safety parameters. Continuous data will be summarized using descriptive statistics including the number of observations, means, standard deviations, medians, lower and upper quartiles, and ranges. Categorical variables will be summarized with frequencies and percentages.

Confidence intervals will be calculated for key parameters or estimates as described in the sections below.

All efficacy parameters will be summarized by descriptive statistics. Two-sided statistical significance testing (alpha level = 0.05) comparing each active treatment to placebo will be performed for the primary and secondary endpoints as described below, unless otherwise noted.

All descriptive statistical analyses will be performed using SAS statistical software (Version 9.3, unless otherwise noted). Adverse events will be coded using the most recent MedDRA version available at the time of analysis. Concomitant medications will be coded using the most recent version of World Health Organization (WHO) Drug.

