### 6.1.10 Determination of Sample Size

The sample sizes for Zogenix Studies 1501 and 1502 were calculated based on the results of two trials with stiripentol reported in the European Public Assessment Report (EPAR) for stiripentol (EMA, 2007). The stiripentol EPAR summarizes the results from two studies: STICLO France and STICLO Italy. In the stiripentol groups, the standard deviation (SD) of the percentage change in seizure frequency from baseline to month 2 was 42% in the French trial and 26% in the Italian trial. The analogous SDs for placebo groups were 38% and 62%. An SD of 50% was assumed for the primary analysis in Protocols 1501 and 1502 that compares ZX008 0.8 mg/kg/day to placebo on the change from baseline in seizure frequency. Using a two-sided test at the  $\alpha=0.05$  significance level, a sample size of 35 subjects per treatment group affords 90% power to detect a difference in mean change from baseline of 40 percentage points. Similar assumptions and calculations yielded a requirement for an additional 35 subjects in the 0.2 mg/kg/day ZX008 group. The total sample size for each study was therefore set at 105 subjects.

In December 2016 results from a double-blind, placebo-controlled Phase 3 study with Epidiolex to treat seizures in Dravet syndrome were presented at the American Epilepsy Society Meeting (<http://ir.gwpharm.com/events.cfm>). In the Epidiolex study, active drug reduced seizures by 39% compared to a reduction of 13% in the placebo. Review of the data suggested that the standard deviation was relatively large, likely above 50% in both treatment groups. In consideration of this new data, the sample size was re-estimated for the ZX008 studies to assume a SD of 55%, higher than the previous estimate of 50%. Other assumptions in the sample size calculation remained unchanged. A sample size of approximately 120 subjects (40 per arm) affords 90% power to detect a difference in mean change from baseline of 40 percentage points with 55% SD. Considering the variability seen in the STILCO and Epidiolex trials, the sample size for Study 1 and Study 2 is set at 120 subjects, 40 per treatment arm. Note that the change in assumed SD was based entirely on data from external trials. Efficacy data from both Study 1501 and 1502 are still blinded and were not used in re-estimating the required sample size.

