### Incidence of Status Epilepticus

The incidence of status epilepticus will be evaluated based on cases captured as such with treatment at hospitals or other treatment centers, those entered as adverse events (including SAEs) into the safety database, and also as convulsive seizures lasting longer than 10 min from the seizure diary. A single seizure meeting more than one of these criteria will be counted once. According to the ILAE, seizures of this duration are to be considered SE.

The number and percentage of subjects with status epilepticus recorded as an AE will be presented by treatment group for the baseline and the T+M period per 28 days.

In addition, the number and percentage of subjects who experience at least one convulsive seizure with duration > 10 min will be reported for the baseline and T+M period.

All seizures recorded in the AE database as status epilepticus should also be included in the seizure diary. An edit check will be performed to identify the overlap between seizures identified as AE of SE and seizures entered into the diary as seizures > 10 min. The "calculated" number and percentage of subjects experiencing SE will be presented by treatment group, defined as individuals who experience either an AE of SE, medical treatment for SE, or a seizure lasting longer than 10 min. Each subject will be represented once regardless of incidence.

A statistical comparison of the differences between the ZX008 0.8 mg/kg/day and placebo groups will be based on a logistic regression model with a categorical response (experienced at least one SE as an AE or a seizure > 10 minutes during T+M, yes or no) as a function of treatment group (active or placebo), age group (< 6 years, ≥ 6 years), and a categorical baseline variable (experienced at least one SE as an AE or a seizure > 10 minutes during Baseline, yes or no). An analogous model will be used to compare the ZX008 0.2 mg/kg/day group to placebo.

The number of incidences of status epilepticus will be cross-tabulated against the incidences of rescue medication uses (Yes/No). Cochran–Mantel–Haenszel test (CMH) test will be used to test the general association between incidences of SE and rescue medication uses.

This document is confidential.

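### Study 1 SAP, section 6.3.3.7: Fisher's exact test does not fit a comparison of status epilepticus episodes per 28 days in which one child may contribute several episodes

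*SAP*

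**What the plan says.** Section 6.3.3.7 of the Study 1 SAP plans several SE analyses. One classifies each child as having SE or not: "Each subject will be represented once regardless of incidence". Fisher's exact test is named for it. The last paragraph then adds an episode analysis: "A second calculation will present the number of incidences of SE, according to the above definition, by treatment group normalized to per 28 days". It states that "In this analysis, a single subject may have more than one episode of SE" and ends with the same test sentence: "Statistical comparisons of the differences between treatment and placebo groups will be based on Fisher's exact test". The SAP does not give the rows, columns or denominators of the table, or say how a rate becomes cell counts. It gives no expected SE rate and no measure of clustering within a child.

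Section 2.3 lists SE incidence among the additional secondary objectives. Section 6.1.1 applies "Two-sided statistical significance testing (alpha level = 0.05) comparing each active treatment to placebo" to primary and secondary endpoints. The six formal tests in section 6.1.2 do not include SE. Section 6.3.3.5 compares another quantity normalised to 28 days, days with rescue medication, by a rank ANCOVA with the child as the unit.

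The Study 2 SAP (section 8.2.2) makes its SE arm comparison with a subject-level logistic regression and names no Fisher test on episode counts.

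**The concern.** Fisher's exact test conditions on the margins of a table of integer counts and takes every counted unit as independent. The episode analysis departs from this in two ways. A count scaled to 28 days is generally not an integer, so it cannot fill a cell without further rules. And if raw episodes are counted instead, a child prone to SE contributes several correlated units.

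The practical risk is that a few children with many episodes produce a small p-value, in either direction, on an endpoint that the SAP lists among those on which superiority is to be shown. Because the table is not defined, two programmers following the SAP could also reach quite different p-values from the same data.

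**Working it through.** **No figure to reproduce.** The SAP states no SE rate, dispersion or error rate. Its only sample-size statement concerns the primary endpoint (section 6.1.10, 40 per arm: "affords 90% power to detect a difference in mean change from baseline of 40 percentage points with 55% SD"). It recomputes correctly, with power 0.902 (normal) or 0.895 (t), but does not bear on SE.

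**Inputs from the SAP.** 40 children per arm (6.1.10), T+M of 14 weeks = 98 days (6.3.1), two-sided 0.05 (6.1.1).

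**Assumptions, not in the SAP.** No treatment effect. Episodes per child are Poisson or negative binomial with mean m = 0.5, 1 or 2 and size k = 1, 0.5 or 0.2, so that variance/mean φ = 1 + m/k. For example, m = 1 and k = 0.5 give φ = 1 + 1/0.5 = 3.

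**Candidate tables**

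- Raw: arm total of episodes over 40 × 98 = 3,920 child-days.
- Scaled: arm total × 28/98, rounded, over 40 × 28 = 1,120.
- Children by number of episodes: 0, 1, 2 or more.
- SE seizures against other convulsive seizures.

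**Simulated type I error (6,000 trials per row)**

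| m | k | φ | Raw | Scaled |
|---|---|---|---|---|
| 0.5 | Poisson | 1 | 0.032 | 0.000 |
| 1 | Poisson | 1 | 0.038 | 0.000 |
| 2 | Poisson | 1 | 0.044 | 0.000 |
| 0.5 | 1 | 1.5 | 0.088 | 0.000 |
| 0.5 | 0.5 | 2 | 0.141 | 0.003 |
| 1 | 1 | 2 | 0.150 | 0.004 |
| 1 | 0.5 | 3 | 0.224 | 0.018 |
| 2 | 1 | 3 | 0.238 | 0.024 |
| 0.5 | 0.2 | 3.5 | 0.252 | 0.021 |
| 2 | 0.5 | 5 | 0.360 | 0.080 |
| 1 | 0.2 | 6 | 0.397 | 0.093 |
| 2 | 0.2 | 11 | 0.544 | 0.234 |

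**Hand check.** A test that assumes φ = 1 has approximate size 2[1 − Φ(1.96/√φ)], where Φ is the standard normal distribution function. At φ = 3 this is 2[1 − Φ(1.13)] = 0.26, and at φ = 11 it is 2[1 − Φ(0.59)] = 0.55, close to the simulated values. Scaling a total by 28/98 divides its variance/mean by 98/28 = 3.5. The scaled table is therefore conservative until φ reaches about 3.5.

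**Other tables.** Children by 0/1/2+ episodes: 0.044-0.050 in all settings. SE against other seizures (assumed 3% SE, mean 30 or 100 seizures per child): about 0.045 with no within-child correlation, 0.10-0.26 at an intraclass correlation of 0.01, 0.30-0.51 at 0.05 and 0.42-0.63 at 0.10.

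**Child-level methods in the same settings.** Wilcoxon on episodes per child 0.042-0.054 (2,000 trials each); Fisher on children with at least one episode 0.023-0.034.

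**Percentages of subjects per 28 days.** The same section also presents percentages of subjects with SE per 28 days. Under a constant hazard (assumed), a 40% risk over the 42-day baseline becomes 1 − 0.6^(98/42) = 69.6% over 98 days. Dividing by time gives 40 × 28/42 = 26.7% against 69.6 × 28/98 = 19.9%, an apparent fall with no change in risk. At a 10% baseline risk the distortion is small: 6.7% against 6.2%.

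**The case against.** The strongest objection concerns size. A reader might infer that the planned test is strongly anticonservative. The SAP does not support that, because it defines neither the table nor the SE rate nor the clustering. Without clustering the raw table holds its level, the scaled table is conservative up to φ of about 3.5, and a table of children by episode count is valid. This stands: the direction of the error cannot be read from the plan. It does not rescue the rule, since leaving the table open is itself the fault.

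Two wider readings also go too far. The paragraph on seizures longer than 10 minutes reports "change from baseline in the number and percentage of convulsive seizures with duration >10 min", and a reader might take Fisher's test there as applied to seizures. The next sentence turns to numbers and percentages of subjects, and the test follows that, so subjects are the natural unit. In the Study 2 SAP a Cochran-Mantel-Haenszel test "will be used to test the general association between incidences of SE and rescue medication uses". That is not an arm comparison and its unit is not stated, so episode-level dependence would be inferred, not shown.

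The consequence is also limited. SE lies outside the six formal tests, section 6.3.1.2 rests efficacy on the primary analysis, and the subject-level SE comparison in 6.3.3.7 is sound. The 42- against 98-day contrast in the percentages affects descriptive comparison with baseline, not the between-arm tests.

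**Conclusion.** The point holds for the last paragraph of section 6.3.3.7 of the Study 1 SAP. Fisher's exact test does not fit an episode rate to which one child can contribute repeatedly, and the p-value is undefined as written. It is anticonservative if clustered raw episodes are treated as independent: 9-54% over the child-day settings examined, against 3-4% for the same table without clustering and at most 2.4% after scaling with φ up to about 3.5. All these figures rest on assumed means and dispersions. What is certain is the mismatch between test and unit; its size is conditional. The primary result, the formal hierarchy and the subject-level SE comparison are unaffected.

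**What to change.** In section 6.3.3.7, make the child the unit for the episode analysis, in one of three ways:

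- Compare per-child SE episodes per 28 days with the rank ANCOVA of section 6.3.3.5 (treatment, rank of baseline rate). That section does not list age; the age stratum may be added.
- Fit a negative binomial model with the log of days observed in the period as offset. Days observed suit the numerator better than diary days, because SE is also counted from hospital treatment and adverse events.
- Report episode rates by arm without a p-value.

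Keep Fisher's test for the subject-level yes/no outcomes. Drop the per-28-days scaling from percentages of subjects there and in the matching section of the Study 2 SAP, and give the percentage with the length of the period.

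The cost is wording and one short program; no new data are needed. The Study 2 SAP says that Study 1 was reported in September 2017, so any episode-level Fisher p-value already issued should be read as descriptive, and a re-analysis labelled post hoc.

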### **6.3.3.8 Duration of Prolonged Seizures**

Duration of convulsive seizures at baseline and on treatment will be presented by treatment group using categories as <2 min, 2-10 min and >10 min.

To obtain a baseline probability distribution for the 3 categories, we will proceed as follows: For each subject, we will calculate the percentage of their total number of baseline seizures that is in each category. (For example, if the subject had 5 seizures, with 2 in the first category and 3 in the last category, their percentage distribution would be 40%, 0%, and 60% in the <2, 2-10, and >10 categories. We can calculate similar numbers for the next subject, and so on.) We will then average these over all subjects to obtain the % of subjects' seizures that were <2 min in duration, the % between 2-10 min in duration, and the % >10 min in duration. These 3 percentages should total 100%. Thus we will obtain a distribution of seizure duration for baseline.

Using the seizure duration data obtained for the T+M period, we will proceed similarly, to obtain a distribution for the T+M period.

It is expected that treatment with ZX008 will result in shorter duration of seizures (as well as fewer seizures) during T+M compared to placebo, i.e., the probability of longer seizures (>10 min) will be higher for the placebo group than for the ZX008 arms. This may be assessed by comparing the probability of a >10 min seizure during T+M to the same during baseline, for a treatment group, to the same for the Placebo group. It is expected that the ZX008 group will have greater odds of a reduction in proportion of seizures >10 min than the Placebo group. However, treatment with ZX008 may result in fewer seizures overall yet the duration of residual seizures may not be shorter. Should the primary or key secondary endpoints be positive for a given dose(s), but the duration of seizures not be shortened per above, exploratory evaluations may be undertaken to better understand the effect.

